4.4. Other Definitions

4.4.1. Bioactivity Measures

Bioactivity measures in this study include CST (μm) and macular volume (mm^3) measured by SD-OCT. Bioactivity of DE-122 will be considered evident if a considerable decrease in CST or macular volume is observed.

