7. INVESTIGATIONAL PLAN

7.1. Overall Study Design and Plan

This is an open-label, dose-escalating, sequential-cohort study assessing the safety, tolerability, immunogenicity, and bioactivity of a single IVT injection of 0.5 mg, 1.0 mg, 2.0 mg and 4.0 mg DE-122 injection administered in a total of approximately 12 subjects with refractory exudative AMD.

Approximately 12 subjects in four cohorts (2 or 3 subjects in Cohort 1, 3 subjects each in Cohorts 2, 3 and 4) will receive a single IVT injection of DE-122 in the study eye. Decisions regarding dose escalation will be based on the recommendations of the Safety Review Team consisting of an external Retina Specialist, the Medical Monitor, and the Drug Safety Physician. Dose-Limiting Toxicity response observed in any cohort will result in termination of the dose escalation.

The study is designed to include up to a 7-day screening phase and 90-day treatment/follow-up phase for each subject.

The first eligible subject in Cohort 1 will receive a single intravitreal injection of 0.5 mg DE-122 in the study eye and will be evaluated through Visit 3 (Day 8±1). The Safety Review Team will review the safety parameters and determine if the safety and tolerability are acceptable.

If acceptable, up to two additional eligible subjects in Cohort 1 will each receive a single intravitreal injection of 0.5 mg DE-122 in the study eye before starting Cohort 2. After the first 2 or 3 subjects in Cohort 1 have completed Visit 5 (Day 30±2), the Safety Review Team will review the safety parameters of the first 2 subjects in Cohort 1 and determine if the next dose (1.0 mg) will be administered to Cohort 2.

The same enrollment procedures will be followed for Cohort 2 (1.0 mg of DE-122), Cohort 3 (2.0 mg of DE-122) and Cohort 4 (4.0 mg of DE-122), however 3 subjects must be enrolled in these cohorts.

Rescue therapy with anti-VEGF medication may be allowed at Visit 3 (Day 8±1) and/or at Visit 7 (Day 60±3) provided the following rescue criteria are met: < 5 letters gained from baseline BCVA or < 50 microns reduction from baseline CST as measured by SD-OCT.

All subjects will receive IVT anti-VEGF treatment at Visit 5 (Day 30±2) after DE-122 IVT injection, in order to avoid a prolonged period without treatment, if no rescue therapy was given at Visit 3 (Day 8±1), regardless of the visual acuity and CST outcomes.

[figure not shown]

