7.6.2.5. Visit 5 (Day 30±2)

- The following assessments must be performed prior to administration of anti-VEGF medication
 - Query for AEs
 - Update medical history and medications
 - Vital signs
 - EKG
 - BCVA (ETDRS)
 - Slit-lamp biomicroscopy
 - IOP
 - Indirect ophthalmoscopy
 - SD-OCT
 - Fundus photography
 - Fluorescein angiography
 - Urinalysis
 - Urine pregnancy test
 - Hematology, chemistry serum sample
 - Immunogenicity serum sample
 - Biomarker serum sample (in Cohorts 3 and 4)
- Upload all collected images (SD-OCT, fundus photograph and fluorescein angiogram) to sponsor.
- Subjects who did not receive rescue therapy with anti-VEGF medication at Visit 3 (Day 8±1) will receive anti-VEGF treatment. The anti-VEGF medication should be performed using the same drug received just prior to enrollment in the study ([Section 9.2.3](#)). If the subject received rescue therapy at Visit 3 (Day 8±1), anti-VEGF treatment and post-injection assessments are not necessary.
- The following assessments must be performed after the administration of anti-VEGF treatment:

- Within 30 minutes following anti-VEGF treatment
 - Slit-lamp biomicroscopy
 - Indirect ophthalmoscopy
- IOP: 40 (± 10) minutes following injection
 - If post-injection IOP is increased ≥ 10 mmHg from pre-injection IOP, the IOP will be measured again 60 (± 10) minutes following injection. If there is an increase of ≥ 10 mmHg at 60 (± 10) minutes post-injection compared to pre-injection IOP, the subject should be prescribed a topical IOP-lowering medication and monitored for resolution of the event by the Clinical Investigator. An IOP increase of ≥ 10 mmHg shall be reported as an AE.
- AE assessments must be performed after the anti-VEGF treatment.
- Schedule the subject to return for Visit 6 (Day 45 \pm 3).

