8.1. Subject Inclusion Criteria

At Screening (Day -7 to Day -1) and Visit 1 (Day 1), subjects must meet all of the following inclusion criteria:

1. Provide signed written informed consent on the IRB / EC approved ICF and provide authorization as appropriate for local privacy regulations.
2. Male or female 50 years of age or older on the date of signing the ICF and able and willing to comply with all treatment and follow-up study procedures.
3. Diagnosis of subretinal or intraretinal fluid secondary to exudative AMD as assessed by SD-OCT in the study eye with a minimum of 300 μm in the central subfield.
4. Prior treatment in the study eye with any intravitreal anti-VEGF medication within the past one year prior to Screening visit (at least 3 anti-VEGF treatments within 6 months or 6 anti-VEGF treatments within 12 months).
5. Treatment with intravitreal injection of anti-VEGF > 30 days and < 60 days from Visit 1 (Day 1).
6. Clinical examination or imaging shows persistent or increasing lesion activity (intraretinal or subretinal fluid, exudation, or hemorrhage) despite continuous anti-VEGF therapy.
7. Total lesion size of ≤ 12 disc areas, contain $\leq 50\%$ hemorrhage and $\leq 50\%$ fibrosis and $\leq 50\%$ retinal pigment epithelial atrophy in the study eye.
8. BCVA of 65 to 20 ETDRS letters (20/50 to 20/400) in the study eye.
9. Fellow eye must have BCVA equal to or better than the study eye, but not worse than 35 ETDRS letters (20/200)
10. Reasonably clear media and some fixation in the study eye to allow for good quality SD-OCT and fundus photography.

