9.2.1. Prohibited Medications or Treatments

Any treatments for exudative AMD in the study eye other than DE-122 are prohibited during the study, except anti-VEGF treatment as a rescue therapy at Visit 3 (Day 8±1) and/or at Visit 7 (Day 60 ±3), and anti-VEGF treatment at Visit 5 (Day 30±2) as described in [Section 9.2.2](#) and [Section 9.2.3](#).

Any systemic treatments with anti-VEGF agents (e.g., bevacizumab) are prohibited during the study.

The decision to administer a prohibited concomitant medication or treatment during the study should be made with the safety of the subject as the primary consideration. Whenever possible, Santen should be notified before any prohibited medication or treatment is administered or if the permissibility of a specific medication or treatment is in question.

9.2.2. Rescue Therapy at Visit 3 (Day 8±1) and/or at Visit 7 (Day 60±3)

Rescue therapy is defined as IVT injection of anti-VEGF medication which is the same medication administered just prior to the enrollment in the study. Rescue therapy with anti-VEGF medication may be allowed at Visit 3 (Day 8±1) and/or at Visit 7 (Day 60±3) provided the following rescue criteria are met: < 5 letters gained from baseline BCVA or < 50 microns reduction from baseline CST as measured by SD-OCT.

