9.2.3. Anti-VEGF treatment at Visit 5 (Day 30±2)

Subjects who did not receive rescue therapy with anti-VEGF medication at Visit 3 (Day 8±1) will receive anti-VEGF treatment at Visit 5 (Day 30±2). The anti-VEGF injection should be performed using the same anti-VEGF medication administered just prior to the enrollment in the study.

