4.2.2. Baseline Score

For any measure, the *baseline score* is the last observed measurement prior to the injection of study medication. For this study, the baseline score would be the measurement prior to the initial injection at baseline visit.

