9. BIOACTIVITY ANALYSES

All bioactivity analyses will be performed on the ITT population. For BCVA, CST and macular volume, scores and changes from baseline will be summarized descriptively by dose level and analysis visit.

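### The SAP lets any considerable fall in CST or macular volume count as DE-122 bioactivity, including falls seen after in-study anti-VEGF injections

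*SAP*

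**What the plan says.** SAP 4.4.1 names CST and macular volume as the bioactivity measures and adds: "Bioactivity of DE-122 will be considered evident if a considerable decrease in CST or macular volume is observed". No other text in either document says when bioactivity is shown. SAP 2.2 takes the CST change at every visit after DE-122. SAP 9 says that for BCVA, CST and macular volume "scores and changes from baseline will be summarized descriptively by dose level and analysis visit". Under SAP 4.2.2 the baseline "is the last observed measurement prior to the injection of study medication", which is the Day 1 pre-injection scan, and SAP 4.2.3 keeps that reference at all later visits.

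The treatment schedule is in the protocol. Section 7.1 says "All subjects will receive IVT anti-VEGF treatment at Visit 5", and the same sentence limits this to subjects not rescued at Visit 3 and makes the injection independent of the acuity and thickness results. Section 9.2.3 agrees. Rescue at Visit 3 and/or Visit 7 is allowed on "< 5 letters gained from baseline BCVA or < 50 microns reduction from baseline CST as measured by SD-OCT" (section 9.2.2). At Visit 5 the scan comes first: "The following assessments must be performed prior to administration of anti-VEGF medication" (section 7.6.2.5).

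Three further provisions bear on the point:

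- Protocol 14.6 promises a summary of the change in retinal thickness after anti-VEGF injection. SAP 9 does not carry it.
- SAP 2.2 refers in parentheses to the response to the anti-VEGF given before Visit 1, and protocol 21.4.1 collects the CST from before that injection. No SAP analysis uses it.
- SAP 6.2 permits LOCF for bioactivity measures and does not mention intervening injections.

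**The concern.** A sentence that calls DE-122 bioactivity evident is a conclusion about DE-122. As written, it can be satisfied by a scan taken after the subject has received another drug that may itself reduce retinal thickness. SAP 1 makes the SAP results the basis of the study report, so the wording matters for how the secondary objective is reported.

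The exposure does not come from a few deviations. Anti-VEGF by Day 30 is built into the schedule for everyone. The exposure is also greatest where DE-122 does least: a subject unchanged at Day 8 meets the rescue criteria, and if rescued then has most of the remaining scans after anti-VEGF. Because the two criteria are joined by *or*, a subject falls outside them only with both a gain of at least 5 letters and a CST reduction of at least 50 microns.

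The by-visit tables do not resolve this. The Day 45 to Day 90 rows reflect DE-122 plus anti-VEGF, and the Day 15 and Day 30 rows can mix rescued and unrescued subjects. LOCF can carry a value from before an anti-VEGF injection into a visit after it.

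**Working it through.** **Inputs.** Visit windows and SD-OCT visits come from the Schedule of Events (protocol Table 4, SAP Table 1): Visit 3 on Days 7–9, Visit 4 on 13–17, Visit 5 on 28–32, Visit 6 on 42–48, Visit 7 on 57–63, Visit 8 on 87–93. Cohort sizes are 2 or 3, then 3, 3 and 3, so N is 11 or 12. Inclusion criterion 5 puts the last pre-study anti-VEGF more than 30 and fewer than 60 days from Visit 1, which is 31–59 whole days.

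**Scan count.** Post-dose scans fall on Days 2, 8, 15, 30, 45, 60 and 90, so there are 7 per subject. The Visit 3 scan precedes rescue, because the rescue criteria use it, and the Visit 5 scan precedes the Visit 5 injection.

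- Not rescued at Day 8: Days 45, 60 and 90 follow anti-VEGF, 3/7 = 43%.
- Rescued at Day 8: Days 15, 30, 45, 60 and 90 follow anti-VEGF, 5/7 = 71%.
- All scans: 7 × 11 = 77 to 7 × 12 = 84.
- After anti-VEGF if nobody is rescued at Day 8: 3 × 11 = 33 to 3 × 12 = 36.
- After anti-VEGF if everybody is: 5 × 11 = 55 to 5 × 12 = 60.

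Only Days 2 and 8 are free of in-study anti-VEGF in every subject.

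**Time since the injection.** The shortest interval is the earliest scan day minus the latest injection day; the longest is the latest scan day minus the earliest injection day. The Day 1 baseline is 31–59 days after anti-VEGF.

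| Injection | Scan | Interval (days) | Against 31–59 |
|---|---|---|---|
| Visit 3 | Day 15 | 13−9 = 4 to 17−7 = 10 | always shorter |
| Visit 3 | Day 30 | 28−9 = 19 to 32−7 = 25 | always shorter |
| Visit 3 | Day 45 | 42−9 = 33 to 48−7 = 41 | inside |
| Visit 3 | Day 60 | 57−9 = 48 to 63−7 = 56 | inside |
| Visit 3 | Day 90 | 87−9 = 78 to 93−7 = 86 | longer |
| Visit 5 | Day 45 | 42−32 = 10 to 48−28 = 20 | always shorter |
| Visit 5 | Day 60 | 57−32 = 25 to 63−28 = 35 | overlaps |
| Visit 5 | Day 90 | 87−32 = 55 to 93−28 = 65 | overlaps the far end |
| Visit 7 rescue | Day 90 | 87−63 = 24 to 93−57 = 36 | overlaps |

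Three scans (Days 15 and 30 after a Visit 3 rescue, Day 45 after a Visit 5 injection) are always nearer to an anti-VEGF injection than the baseline scan was. At those scans, change from baseline partly compares different points in an anti-VEGF cycle. The other rows do not show that imbalance consistently, but they still follow in-study anti-VEGF.

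**What is not computed.** The documents give no anti-VEGF effect on CST, no SD, no threshold for *considerable* and no rescue rate. No probability of a wrong *evident* call can be derived from them, and none is claimed.

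**The case against.** The strongest reply is that SAP 4.4.1 sits among definitions and mainly gives the favourable direction. The study has no hypothesis (protocol 14.1.3), every summary is descriptive, and no planned table produces an *evident* call. That limits the harm to interpretation; there is no type I error to inflate. But a statement that bioactivity is evident is still a conclusion, and without a threshold it is easier to reach.

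Second, the subjects are refractory, in-study anti-VEGF is the same product they had before, and protocol 5 proposes synergy with anti-VEGF. Scans after anti-VEGF may therefore be part of the intended question. This has weight. However, inclusion criterion 6 requires persistent or increasing activity on treatment, not the absence of any thickness response. A question about the combination also needs comparison with the subject's own earlier anti-VEGF response, which SAP 2.2 mentions and no analysis delivers.

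Third, tables are by visit, injection dates are recorded and listings are planned. A careful reader could isolate Days 2 and 8 and reconstruct anti-VEGF status for 11 to 12 subjects. True, but the SAP does not direct this, and knowing the status does not separate the two effects at Days 45 to 90.

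Fourth, protocol 14.6 remains in force. It does, but the SAP omits its summary, and that summary would not restrict SAP 4.4.1.

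The timing argument applies to only some scans: one of three in an unrescued subject, two of five in a rescued one. It supports the point and does not carry it.

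**Conclusion.** The concern holds. Nothing in the SAP limits the bioactivity statement by visit or anti-VEGF status, and between 43% and 71% of each subject's post-dose scans follow in-study anti-VEGF, depending on rescue at Day 8. This assumes scheduled scans all obtained and treatment per protocol. An anti-VEGF effect can be credited to DE-122 on the secondary objective. Safety conclusions and dose escalation are unaffected. It should be corrected before database lock.

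**What to change.** Change the SAP only; treatment and rescue stay as they are.

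1. In 4.4.1, confine any statement about DE-122 alone to scans before the subject's first in-study anti-VEGF injection, with the Day 8 pre-rescue scan, scheduled in everyone, as the main time point. Before database lock, state what decrease counts as *considerable*, or drop *evident* and report values only.
2. In SAP 9, show Days 15 and 30 for all subjects and split by Day 8 rescue status, noting that unrescued subjects may be selected on their Day 8 response.
3. Label every value after the first in-study anti-VEGF injection as DE-122 plus anti-VEGF, and restore the protocol 14.6 summary.
4. List, within subject, the CST change after the last pre-study anti-VEGF (pre-injection value to Day 1) beside the change after in-study anti-VEGF. Give both intervals: 31–59 days pre-study and, for example, 25–35 days from Visit 5 to Visit 7 or 33–41 from Visit 3 to Visit 6.
5. Do not carry a value forward across an anti-VEGF injection.

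The cost is SAP wording, a status label, one restored summary and one listing; no new visits or tests. There are drawbacks. Fewer scans support the DE-122-alone statement: Days 2 and 8, plus Days 15 and 30 in unrescued subjects. That subset may favour DE-122. In item 4, the pre-study CST has no stated scan date, and its device may differ because the same-machine rule (protocol 21.4.9) covers only the study. Without a control arm the result stays descriptive and natural variation cannot be excluded.

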4.4.2. Immunogenicity

ADA titer will be measured in serum samples collected at Visit 1 (Day 1) and Visit 5 (Day 30 \pm 2).

4.4.3. Biomarker

Serum samples will be collected in Cohorts 3 and 4, and measured for levels of endoglin-related proteins. Changes from baseline in levels of biomarkers will be summarized descriptively by dose level of DE-122.

5. STUDY POPULATION

5.1. Intention-to-Treat Population

The Intention-to-Treat (ITT) Population will include all subjects in the study.

6. GENERAL CONSIDERATIONS

Besides data listings, all measures will be summarized by dose level and/or overall. Continuous variables will be summarized using descriptive statistics such as number of observations (n), mean, standard deviation, minimum, and maximum. Categorical variables will be tabulated using frequency (n), sometimes along with percentage (%). Percentages will not be displayed for summaries by dose level due to the small sample size.

All data manipulations and descriptive summaries will be implemented using SAS[®], Version 9.3 or later.

6.1. Adjustments for Covariates

Covariate adjustments are not applicable to this study.

6.2. Handling of Missing Data

For safety measures, missing scores will not be imputed for data summaries.

For bioactivity measures, the last-observation-carried-forward (LOCF) approach may be used to impute missing post-injection values. However, baseline scores will not be carried forward.

Completely or partially missing onset and resolution dates of medical events including AEs will be conservatively imputed as follows:

Date	Type of Missing Date	Handling of Missing Date
Event onset date (e.g., YYYY-MM-DD)	Completely missing	No imputation will be applied.
	Only YYYY is available	Use the first day of YYYY to impute the missing month and date parts of the onset date
	YYYY and MM are available but DD is missing	Use the first day of MM to impute the missing date part of the onset date
Event resolution date (e.g., YYYY-MM-DD)	Completely missing	No imputation will be applied.
	Only YYYY is available	Use the last day of YYYY to impute the missing month and date parts of the resolution date
	YYYY and MM are available but DD is missing	Use the last day of MM to impute the missing date part of the resolution date

Same rules will be followed to impute completely or partially missing start and end dates of non-study medications.

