14.3. Handling of Missing Values

For safety measures, missing scores will not be imputed for data summaries.

Completely or partially missing onset and resolution dates for AEs and completely or partially missing start and end dates of concomitant medications will be imputed in a conservative fashion that will be detailed in the SAP.

For Bioactivity endpoints, missing post-injection values will be imputed using the last-observation-carried-forward (LOCF) approach.

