8.2. Best Corrected Visual Acuity

BCVA scores and changes from baseline in BCVA score will be summarized by dose level and analysis visit. The overall number and proportion of subjects maintaining vision will be obtained.

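### LOCF for CST and macular volume is required by the protocol but optional in the SAP, and neither document stops a value being carried across an on-study anti-VEGF injection; whether BCVA is imputed is left unclear

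*SAP*

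**What the plan says.** **Missing bioactivity values.** Protocol 14.3: "For Bioactivity endpoints, missing post-injection values will be imputed using the last-observation-carried-forward (LOCF) approach". SAP 6.2, on bioactivity measures, says the LOCF "approach may be used to impute missing post-injection values. However, baseline scores will not be carried forward". The second sentence of that quote is a limit that the protocol lacks. The SAP does not explain the change from required to optional, and does not say when LOCF would be used, who decides, or by when.

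**Missing safety values.** Both documents rule out imputation. SAP 6.2: "For safety measures, missing scores will not be imputed for data summaries".

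**What counts as bioactivity.** Protocol 14.1.1 and SAP 4.4.1 name CST and macular volume only. BCVA is a safety endpoint in Protocol 14.1.1 and a safety measure in SAP Table 2.

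**Where BCVA is analysed.** SAP 8.2, under safety: "BCVA scores and changes from baseline in BCVA score will be summarized by dose level and analysis visit". SAP 9, under bioactivity: "For BCVA, CST and macular volume, scores and changes from baseline will be summarized descriptively by dose level and analysis visit". Protocol 14.6 also places BCVA in the bioactivity analyses.

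**Anti-VEGF on study.** Under Protocol 9.2.2 and 9.2.3, rescue may be given at Visit 3 (Day 8) and/or Visit 7 (Day 60). Subjects not rescued at Visit 3 receive anti-VEGF at Visit 5 (Day 30).

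**The concern.** There are three linked problems.

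1. **The choice is open.** A discretionary imputation rule in an open-label study lets the analyst decide on LOCF after seeing which values are missing and what the neighbouring values look like. SAP section 1 requires deviations from the SAP to be justified in the study report. Under an optional rule, neither using LOCF nor omitting it is a deviation, so nothing has to be explained. SAP 4.1.3 handles a similar choice better: widened analysis windows are decided by named roles before database lock.

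2. **LOCF does not suit this treatment sequence.** It presumes that a subject's value would have stayed roughly where it was. Here the treatment of the study eye changes during follow-up, and a carried value can sit on the wrong side of that change.

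3. **BCVA falls under two headings with opposite imputation rules.** A programmer cannot tell from the SAP whether the section 9 BCVA summary is imputed.

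At stake is the reading of cohort mean CST and macular volume at the later visits, and the consistency of two summaries of the same BCVA data.

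**Working it through.** **Planned size.** The documents give one design figure, approximately 12 subjects. The cohorts sum to 2 + 3 + 3 + 3 = 11 or 3 + 3 + 3 + 3 = 12, which agrees. No hypothesis, power or effect size is defined, so there is no other figure to reproduce.

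**How a value crosses an injection.** Protocol 7.6.2.5 places the Visit 5 SD-OCT before that visit's anti-VEGF injection. At Visits 3 and 7 the rescue criteria use CST, so the scan must come before rescue wherever CST is the ground for it. Scans at these visits are therefore normally pre-injection values, and one missed scan is enough:

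- Visit 6 missed after anti-VEGF at Visit 5: the Day 30 pre-injection value is reported at Day 45.
- Visit 4 missed after rescue at Visit 3: the Day 8 pre-injection value is reported at Day 15.
- Visit 8 missed after rescue at Visit 7: the Day 60 pre-injection value is reported at Day 90.

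The opposite can also happen: a value taken soon after anti-VEGF can be carried to a visit by which the response may have waned. The only carry-forward barred in either document is that of baseline, in SAP 6.2.

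**Weight of one carried value.** Shift in the cohort mean = (carried value − true value) / n. The weight is 1/3 = 33% for n = 3 and 1/2 = 50% for n = 2. If a cohort of 3 gains a replacement subject (Protocol 8.3) and all subjects are kept in the ITT population, it is 1/4 = 25%. The documents give no size for the error, so the range below is assumed.

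| Assumed error in the carried CST (µm) | Shift, n = 3 (µm) | Shift, n = 2 (µm) |
|---|---|---|
| 25 | 25/3 = 8.3 | 25/2 = 12.5 |
| 50 | 50/3 = 16.7 | 50/2 = 25 |
| 100 | 100/3 = 33.3 | 100/2 = 50 |

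**LOCF against observed cases, constructed example.** Take n = 3, with observed Day 60 CST changes of −60 and −80 µm. The third subject is last scanned at Day 15 with a change of −10 µm, so the Day 30, 45 and 60 scans are all missing.

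- LOCF mean: (−60 − 80 − 10)/3 = −50 µm.
- Observed-case mean: (−60 − 80)/2 = −70 µm.

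| Assumed true Day 60 change, third subject (µm) | Full-data mean (µm) | LOCF error (µm) | Observed-case error (µm) |
|---|---|---|---|
| −10 | −150/3 = −50 | 0 | −20 |
| −60 | −200/3 = −66.7 | +16.7 | −3.3 |
| −110 | −250/3 = −83.3 | +33.3 | +13.3 |

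Neither summary is always closer to the truth.

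**How often it could arise.** The documents give no missing-data rate. With an assumed independent rate d per subject at a visit, the chance of at least one missing value in a cohort of 3 is 1 − (1 − d)³. This is 14%, 27% and 49% for d = 5%, 10% and 20%. Among 12 subjects, 1 − (1 − d)¹² gives 46%, 72% and 93%.

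**BCVA.** The LOCF sentences apply to bioactivity endpoints (protocol) and measures (SAP), both defined without BCVA. Read literally, BCVA is a safety measure and is not imputed. The contrary reading rests only on its appearance in Protocol 14.6 and SAP 9.

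**The case against.** The strongest case on the other side is that only a wording conflict survives.

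- **Little hangs on it.** Bioactivity is secondary, no hypothesis is tested, and escalation and termination rest on safety criteria. This stands, and it limits the severity.
- **Missing values are partly guarded against.** Protocol 8.3 asks for the exit assessments on the day of discontinuation and allows replacement. This reduces long carry-forwards after dropout, but does nothing for a single missed visit.
- **The data are already visible.** The number of observations is a planned statistic and all parameters are listed. But with LOCF that number can include imputed values, and no count of them is planned. Protocol 14.6 also promises a summary of retinal thickness change after anti-VEGF, but SAP 9 does not carry it over.
- **A 33–50% weight comes from the small cohorts.** True: an observed value weighs the same. The difference is that a carried value was not measured at that visit.
- **Observed cases are not necessarily more accurate.** This stands. In the first row of the example LOCF is exact and the observed-case mean is off by 20 µm. Observed values at Visits 6 to 8 also follow anti-VEGF, so dropping LOCF does not remove that confounding.

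A reader might also infer more than the documents support. They do not show that LOCF is applied to BCVA, since both definitions of bioactivity leave it out. They do not show a bias of known direction or size, because they give no missing-data rate, CST variability or anti-VEGF response. Nor is the 50 µm rescue criterion a yardstick for a cohort mean, since it is an individual subject's change from baseline.

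**Conclusion.** The point holds in a limited form. The two documents conflict on whether LOCF is required, and the SAP leaves its use to a choice that may follow sight of the data. Nothing in the documents shows that such a choice was made; the defect is that the plan permits it. Neither document prevents CST or macular volume from being carried across an on-study anti-VEGF injection, and one missed scan can be enough. At planned cohort sizes one such value is 33–50% of the mean. For an assumed error of 25–100 µm, the mean CST change moves by 8.3–33.3 µm (n = 3) or 12.5–50 µm (n = 2), in either direction. BCVA's imputation status is ambiguous, so a difference between its two summaries is possible but not established.

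Severity is minor to moderate: the objective is secondary, the analysis is descriptive, and individual listings are planned.

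**What to change.** - In both Protocol 14.3 and SAP 6.2, make observed cases the main summary of CST and macular volume, with n shown at each visit.
- If LOCF is kept, label it supplementary, do not carry a value across an anti-VEGF injection, and show the number of imputed values at each visit.
- State that BCVA is not imputed in either the SAP 8.2 or the SAP 9 summary. The two summaries can both stay, since they use different analysis populations.
- In the listings, flag each value as before or after on-study anti-VEGF. Base the flag on the order of scan and injection, because at an injection visit the visit number alone does not settle it.

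The cost is a wording change and a small amount of programming. n may fall by one at some visits, and an observed-case mean can itself be off when the missing subject differs from the others. The gain is a rule fixed in advance and main summaries that contain only measured values.
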